6.5.2 Auto-stem cell infusion and recovery

Pediatric and adult guidelines for preventing and managing complications of autologous HSC transplant patients in effect at the time of treatment should be followed and may supersede the following recommendations.

- 6.5.2.1 Blood component support. All blood products will be irradiated to prevent graft-versus-host disease. Transfusions with leukocyte-poor packed red blood cells will be given as needed to maintain the hematocrit greater than 25%. Platelets will be given as needed to maintain the platelet count above 10,000, or higher as clinically indicated.
- 6.5.2.2 Infectious prophylaxis. Patients should be given prophylaxis against mycotic disease from Day 1 through Day 75. Suspected or documented fungal infections should be promptly treated according to standards for transplant recipients. Patients

should receive effective prophylaxis for *Pneumocystis carinii* pneumonia, from Day 1 until 6 months after treatment is completed.

6.5.2.3 Management of fever. Management of fever in neutropenic patients will be according to practice guidelines for the bone marrow transplant service. Broad spectrum antibiotics will be initiated, after appropriate cultures are obtained, for any fever >38.5°C. Persistent unexplained fever will be treated as a presumptive invasive fungal infection.

6.5.2.4 Immunizations. Patients will not receive any immunizations for at least 6 months after completion of therapy. They will not receive any live viral vaccines until appropriate T lymphocyte counts and responses to diphtheria and tetanus vaccines have been demonstrated. Immunization of household members for influenza in the first two years after treatment will be recommended as for households of autologous BMT recipients.

6.5.3 Concomitant medications

While on study care should be taken to avoid medications that potentially will worsen pancytopenias or hypocalcemia. Additionally, patients may not receive bisphosphonate therapy while on trial.

6.5.4 Radiation therapy.

Complete consent and counseling will be specific to the radiation site and plan, and will be administered by treating radiation oncologist.

7.0 TOXICITY AND COMPLICATIONS

7.1 IFOSFAMIDE: Nausea, vomiting, anorexia, anemia, leucopenia, thrombocytopenia, hair loss, arrhythmia (rare), sleepiness, confusion (rare), seizures (rare), electrolyte imbalance, hemorrhagic cystitis, renal failure or insufficiency, myocardial necrosis (rare), scarring of the bladder or lungs, infertility, and second malignancy (very rare).

7.2 MESNA: Nausea, vomiting, stomach pains, headache, diarrhea, allergic reactions, and pains in the arms, legs, and joints (all very rare).

7.3 ¹⁵³Sm-EDTMP: Pain at the tumor site, slow bone growth (rare) or bone deformity (rare). The EDTMP component may cause hypocalcemia and may very rarely cause reactions such as wheezing, low blood pressure, hives, or trouble breathing.

7.4 STEM CELL INFUSION: Hypertension, nausea, bradycardia, garlic-like odor to the breath (all due to residual DMSO used as a cryopreservative).

7.5 G-CSF: headache, fever, chills, decreased appetite, pains in bones, chest, belly or joints, and rash.

7.6 EXTERNAL BEAM RADIOTHERAPY: The specific risks associated with external beam radiotherapy depend on the sites to be treated and the techniques that are used. These will be discussed in detail at the time of treatment by the radiation oncologist.

8.0 AGENT INFORMATION

8.1 ¹⁵³SM-EDTMP

¹⁵³Samarium is a beta- and gamma-emitting lanthanide element. It has 3 principal beta emissions of 640 keV, 710 keV, and 810 keV maxima. These medium energy beta particles are tumoricidal. It also emits a gamma photon of 103 keV that allows for scintigraphic imaging. ¹⁵³Samarium is chelated with EDTMP (also known as lexidronam), a bone seeking tetraphosphonate compound. The chelated complex, ¹⁵³Sm-EDTMP, is supplied sterile and pyrogen-free from the manufacturer (EUSA Pharma) under the trade name Quadramet. It is dissolved in a saline solution (typically 10 ml total volume) that is infused intravenously over a 1-2 minute period.

8.2 IFOSFAMIDE (IFEX)

NSC-109724. Commercially available.

Formulation: Lyophilized powder, 1 g and 3 g per vial.

Storage: Room temperature. *Reconstitution:* Reconstitute 1 gm vial with 20 ml sterile water and 3 g vial with 60 ml sterile water, to a final concentration of 50 mg/ml. Further dilution with NS, D5W, or Lactated Ringer's is acceptable. *Stability:* Discard reconstituted drug after one week at 30° or 3 weeks at 5°C.

Toxicities: Myelosuppression. Alopecia. Nausea and vomiting. Hemorrhagic cystitis, and acute tubular necrosis. Lethargy, confusion, somnolence, excitement, disorientation, and hallucination. Transient liver function abnormalities.

8.3 MESNA (SODIUM 2-MERCAPTOETHANESULFONATE)

NSC-113891. Commercially available.

Formulation: 1,000 mg/10 mL multidose vials which contain 10.4 mg/mL of benzyl alcohol as a preservative.

Storage: Room Temperature. *Reconstitution:* Dilution of Mesna with NS, D5W, or Lactated Ringer's is acceptable. *Stability:* MESNA is not light-sensitive, but is oxidized to diMESNA when exposed to oxygen. Non-preserved ampules should be used immediately after opening, while benzyl alcohol-preserved vials may be stored and used for 8 days. After further dilution for administration, either product is chemically stable for at least 24 hours. Lack of an antimicrobial preservative suggests that the non-preserved product should be used within 6-8 hours after diluted for administration. *Toxicities:* Bad taste in the mouth, nausea and vomiting, diarrhea. Young children receiving high doses of benzyl alcohol (> 99 mg/kg/day) may develop the gasping syndrome manifested by gasping, metabolic acidosis and multiple

organ system failure. Benzyl alcohol is the preservative in multidose vials of MESNA. It results from inability to adequately conjugate benzoic acid with glycine, a metabolic pathway poorly developed under 8 weeks of age.

9.0 TREATMENT EVALUATION

9.1 DEFINITIONS

9.1.1 Radiologic Response

9.1.1.1 Complete response: Complete resolution of all disease by radiologic imaging (CT or MRI).

9.1.1.2 Partial response: > 50% reduction in the sum of the products of perpendicular tumor diameters.

9.1.1.3 Minor response: A 25-50% reduction in the sum of the products of the tumor diameter without the emergence of new lesions. No individual lesion progressing more than 25% in a single dimension

9.1.1.4 Stable disease: No progressive disease.

9.1.1.5 Progressive disease: Emergence of new lesions or progression of any lesion by more than 20% in a single dimension.

9.1.2 Histologic Response

9.1.2.1 Complete response: 100% necrosis.

9.1.2.2 Good response: $\geq 90\%$, but $< 100\%$, necrosis.

9.1.2.3 Poor response: $< 90\%$ necrosis.

9.1.3 Clinical Response

Patients will be considered a clinical response if they have stable disease or any radiologic response by RECIST 1.1 criteria. Dates of progression or death will also be recorded in order to calculate progression-free and overall survival. Toxicities will be graded according to the Bearman criteria for bone marrow transplant studies and according to the NCI Common Terminology Criteria for Adverse Events version 4.0.

9.2 CRITERIA FOR REMOVAL FROM STUDY

Patients will be removed from the study for patient or parent choice, or for excessive toxicity at the discretion of the principal investigators.

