3.2 SECONDARY OBJECTIVES

3.2.1 To describe the toxicity and long-term effects of combined infusional ^{153}Sm -EDTMP and external beam radiation therapy.

3.2.2 To image tumors using [^{18}F]Fluoromisonidazole (^{18}F -MISO) PET scanning before and after treatment, and compare with clinical response as measured by radiographic imaging and/or histology.

3.2.3 To describe the distribution of absorbed doses delivered to each targeted lesion and the distribution of lesion equivalent uniform dose delivered to each patient.

3.2.4 To determine dosimetry measurements after initial tracer dosing, predict target total radiation exposure to tumor based on linear kinetics previously described, and calculate a subsequent combined treatment dose.

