6.3 ON-STUDY EVALUATION

- 6.3.1 Dosimetric studies by ^{153}Sm SPECT/CT to be assessed at approximately 4, 24, and 48 hours after injection of tracer dose of ^{153}Sm -EDTMP; SPECT/CT will also be collected at approximately 4, 24, and 48 hours following the therapeutic administration of ^{153}Sm -EDTMP. Scans can be obtained at any time on the first and second day after infusion of ^{153}Sm -EDTMP, as long as the specific number of hours post-infusion is recorded.
- 6.3.2 Complete evaluation, including history and physical exam, vital signs, weights, and laboratory evaluation including complete blood counts and a complete metabolic panel, Mg and Phosphorous to be performed weekly until hematopoietic recovery and until recovery from therapy-related toxicities.
- 6.3.3 Because of the risk of renal and bladder toxicity from the excretion of ^{153}Sm -EDTMP that is not adsorbed to tumor, care will be taken to monitor patients closely for urinary tract toxicity. Prior to treatment, patients will have a complete urinalysis, measurement of BUN and creatinine, and 24- hour urine collection for creatinine clearance. These tests will be repeated as clinically indicated based on urinary symptoms and at the completion of therapy.
- 6.3.4 Restaging evaluation to include radiologic imaging by CT or MRI of the primary tumor and metastases, follow up [^{18}F]-MISO/[^{18}F]-FDG PET, plain radiographs of primary lesion, and Tc-99m bone scan. These studies will occur approximately one month after completion of external beam radiotherapy. Based on our prior experience with [^{18}F]-FDG PET and the lack of correlation between clinical response and SUV levels, we will not use [^{18}F]-MISO/[^{18}F]-FDG PET SUVmax measurements to determine clinical response while the patient is receiving treatment.

- 6.3.5 CT scan of chest and Tc-99m bone scan every 4 months after completion of therapy for one year, then every 6 months for 1 year, and then yearly for 3 years. Thereafter scans will be repeated only as clinically indicated.
- 6.3.6 Evaluation for long-term skeletal toxicity will be performed every 6 months for the first 4 years after completion of therapy, and will include alkaline phosphatase and LDH (bone fractions), serum C-telopeptide and parathyroid hormone levels, and bone density scans.
- 6.3.7 If any lesions are resected after patient has completed radiation therapy, percent necrosis will be determined by the pathologist and recorded.

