11.0 STATISTICAL CONSIDERATIONS

11.1 OVERVIEW

This protocol will assess the proportion of clinical tumor responses, defined as progression-free survival at 6 months, and the toxicities associated with high-dose ^{153}Sm -EDTMP (MTD at 30 mCi/kg) after an initial lower dose of the agent along with external beam radiation therapy in patients with high-risk osteogenic sarcoma.

Primary objective: The primary objective of this study is to determine if the addition of external beam radiation therapy to infusional ^{153}Sm -EDTMP can delay the progression of target lesions. The primary endpoint is 6-month progression free survival (PFS). It is a combined effect of the entire treatment. To be evaluable, patients must meet all eligibility criteria, including signing a consent form, and have completed treatment according to protocol without major deviations. Patients who are enrolled but unevaluable will be replaced on the study. Only patients enrolled on Stratum 1 (i.e., with a diagnosis of osteosarcoma) will be evaluated for the Primary Objective.

Secondary objectives:

1. Describe the short and long-term toxicity profile of combined treatment with ^{153}Sm -EDTMP and external beam radiation therapy.
2. Estimate the local control rate. (Stratum 1 only)
3. Determine the overall survival (OS). (Stratum 1 only)
4. Describe the distribution of absorbed doses delivered to each targeted lesion and the distribution of equivalent uniform doses delivered to each patient.
5. Model the relationship between absorbed doses and time to progression.
6. Determine the correlation of hypoxic volume and maximum tumor/blood ratio obtained by [^{18}F]-MISO PET scanning with patient outcomes.

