11.2 STUDY DESIGN

This is a single-arm study with 2 strata: Stratum 1 for patients with osteosarcoma, and Stratum 2 for patients with other high risk solid tumors. Stratum 2 is exploratory in nature, and the goal of including these patients is to facilitate accomplishing secondary objectives related to toxicity and the feasibility of administering this treatment regimen to solid tumor patients. If possible, we will, however, use patients on Stratum 2 to estimate response rates of tumors other than osteosarcoma. For Stratum 1, 6-month PFS as the primary endpoint. The study will pre-specify target lesions for each patient in Stratum 1 that will be used to assess PFS, with the intention that every lesion radiographically evident at the time of enrollment will be a target lesion. Events will be the first disease progression at any of the target lesions or death from any cause. All patients treated on Stratum 1 will be included in the determination of PFS, regardless of treatment modification or discontinuation. The design will include interim analyses for futility if it seems unlikely that the treatment has sufficient activity. The historical PFS in 11 patients treated with ¹⁵³Sm-EDTMP similar to how we are proposing, but without the external beam component, was 15.8%. For this study of ¹⁵³Sm-EDTMP plus external beam radiation therapy, a 6-month PFS of 35% would be the lowest that would be considered acceptable, and PFS that is convincingly worse than this would be considered grounds for discontinuing further study. The non-parametric Kaplan-Meier estimate will be used to monitor the PFS function. After 8 patients have been enrolled, the design will include an interim analysis for futility that could halt the trial if it seems likely that this regimen does not have sufficient clinical activity. The study is designed to stop if we are 80% certain that the 6-month PFS is below 15%.

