Survival curves will be estimated by using the Kaplan-Meier method. Progression-free survival is defined as time from registration to the first observation (documentation) of disease progression or death. Patients who are lost to follow-up will be censored for determination of PFS on the date of their last evaluations. Overall survival is defined as time from registration to death due to any cause.

11.3.6 Determine correlation of hypoxic volume and maximum tumor/blood ratio obtained by [¹⁸F]-MISO PET scanning with patient outcomes.

Cox regression analysis will be performed to measure association between hypoxia based on HV and max T/B ratio with Kaplan-Meier survival and time-to-progression curves. Additional regression analysis will be performed to evaluate the link between hypoxic indices and uptake of ¹⁵³Sm-EDTMP and clinical response based on radiologic response and presence of necrosis on histology.

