12.0 DATA RECORDING, MANAGEMENT, AND MONITORING

12.01 To register eligible patients on study, the investigator will fax the completed registration form to the Johns Hopkins Oncology center Clinical Research Office at [contact].

12.02 Informed consent must be signed by the patient or in the case of a minor, the parent or legal guardian.

12.03 If a patient does not receive protocol therapy, the patient is removed from protocol. Reasons for cancellation must be submitted in writing to the Principal Investigator. Once a patient has been given protocol treatment, all forms must be submitted.

12.04 Case report forms, including dosimetry, toxicity and response evaluation will be completed in a timely manner.

12.05 This is a DSMP Level I study under the SKCCC Data Safety Monitoring Plan (12/6/2012). The Clinical Research Office QA Group will perform an audit after the first subject has been treated and then periodically depending on the rate of accrual and prior audit results. All trial monitoring and reporting will be reviewed annually by the SKCCC Safety Monitoring Committee.

The PI is responsible for monitoring the study. Data must be reviewed to assure the validity of data, as well as, the safety of the subjects. The PI will also monitor the progress of the trial, review safety reports, and clinical trial efficacy endpoints and to confirm that the safety outcomes favor continuation of the study.

The PI will be responsible for maintaining the clinical protocol, reporting adverse events, assuring that consent is obtained and documented, reporting of unexpected outcomes, and reporting the status of the trial in the continuing renewal report

submitted to the IRB and to the trial monitoring review group. Content of the continuing renewal report at a minimum should include year-to-date and full trial data on: accrual and eligibility, protocol compliance, treatment administration, toxicity and ADR reports, response, survival, regulatory compliance, compliance with prearranged statistical goals. The report should be submitted in a timely manner according to the schedule defined by Johns Hopkins Medicine Institutional Review Board.

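### Section 9.2 takes patients with excessive toxicity off the study without saying that follow-up continues, which leaves late-toxicity data unprotected and their place in the PFS analysis unresolved

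*Combined protocol and SAP*

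**What the plan says.** Section 9.2 is one sentence: "Patients will be removed from the study for patient or parent choice, or for excessive toxicity at the discretion of the principal investigators". It names two routes out, choice and toxicity, and gives both the same consequence. Neither 9.2 nor any other section describes a patient who has stopped protocol treatment but is still followed on study.

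The plan nevertheless depends on long follow-up. Objective 3.2.1 is "To describe the toxicity and long-term effects of combined infusional" treatment and external beam radiotherapy, and 11.1 repeats long-term toxicity as its first secondary objective. Section 6.3.6 provides the main skeletal data: "Evaluation for long-term skeletal toxicity will be performed every 6 months for the first 4 years after completion of therapy". Section 6.3.5 schedules chest CT and bone scans over five years, and Table 2 in 6.4 adds creatinine clearance and bone density.

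Three sections bear on PFS:
- 11.2: "All patients treated on Stratum 1 will be included in the determination of PFS, regardless of treatment modification or discontinuation".
- 11.1: to be evaluable, patients must "have completed treatment according to protocol without major deviations", and "Patients who are enrolled but unevaluable will be replaced on the study".
- 11.3.5: "Patients who are lost to follow-up will be censored for determination of PFS on the date of their last evaluations".

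Section 12.03 adds: "Once a patient has been given protocol treatment, all forms must be submitted".

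**The concern.** Patients who come off for toxicity are among the most informative for a description of late effects. If their renal, skeletal and imaging assessments stop at removal, later events in them go unrecorded, and the long-term profile is built mainly from patients who tolerated the regimen. The direction of that loss is towards too favourable a profile.

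For PFS, the question is what happens to a Stratum 1 patient who leaves under 9.2 before progressing. Depending on which section the analyst follows, that patient is followed to an event, censored, or declared unevaluable and replaced. If removal for toxicity goes with a worse outlook, the last two choices raise the estimated 6-month PFS, which is the primary endpoint in section 11.

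**Working it through.** **1. Does any other section keep these patients in late-toxicity follow-up?**
- 6.3.2 requires weekly evaluation until blood counts and treatment-related toxicities recover. It covers acute toxicity and then ends.
- 6.3.6 is timed from completion of therapy. A patient stopped early may never reach that point, so the schedule has no defined start.
- 12.03 requires all forms after treatment has begun. It does not say that visits or scans take place after removal.
- 9.1.3 records dates of progression and death, but progression cannot be dated without imaging.
- 11.2 keeps treated patients in the analysis whatever happens to treatment, but only for Stratum 1 and only for PFS. It says nothing on late toxicity or on Stratum 2, which 11.2 includes partly for the toxicity objectives.

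None of these fills the gap for late effects.

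**2. The plan's own power figure.** Inputs from 11.3.1: reference 6-month PFS 15.8%, benchmark 35%, 20 patients, one-sided alpha 0.05, five years of accrual plus one year of follow-up, exponential PFS.
- Reference hazard: -ln(0.158)/6 = 0.308 per month. Benchmark hazard: -ln(0.35)/6 = 0.175. Ratio: 1.76.
- Exact chi-square test on total time at risk with 20 events: power 82.3%, which reproduces the stated 82%.
- Normal approximation, Phi(sqrt(d) x ln 1.76 - 1.645): 81.1% at d = 20, and 80.7% at the 19.8 events expected under the accrual plan.

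**3. Loss of events if removed patients are censored.** The documents give no removal share, so the shares and the removal time (month 1 to 3) are assumptions. Expected events = (1 - f) x 19.8 + 20f x (1 - exp(-0.175t)), with power from the normal approximation.

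| Share removed (f) | Expected events | Power |
|---|---|---|
| 0 | 19.8 | 81% |
| 5% | 18.9-19.2 | 79-80% |
| 10% | 18.1-18.6 | 78-79% |
| 16.7% | 17.0-17.8 | 75-77% |
| 30% | 14.8-16.3 | 70-74% |

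**4. Bias in 6-month PFS.** Assume that a share f would be removed at month 1.5, with hazard k times that of the others (b), and that true overall 6-month PFS is 15.8%.
- Solve (1 - f) x exp(-6b) + f x exp(-6kb) = 0.158 for b.
- Kaplan-Meier if censored at removal: [(1 - f) x exp(-1.5b) + f x exp(-1.5kb)] x exp(-4.5b).
- If the whole group is excluded and replaced by patients who complete treatment: exp(-6b).

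Worked case, f = 0.30 and k = 2: b = 0.262. Censored: (0.7 x 0.675 + 0.3 x 0.455) x 0.307 = 0.187. Excluded: 0.207.

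| f | k | Censored | Excluded and replaced |
|---|---|---|---|
| any | 1 | 15.8% | 15.8% |
| 10% | 2 | 16.6% | 17.2% |
| 10% | 3 | 16.5% | 17.5% |
| 20% | 2 | 17.6% | 18.9% |
| 20% | 3 | 17.4% | 19.6% |
| 30% | 2 | 18.7% | 20.7% |
| 30% | 3 | 18.6% | 22.1% |

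Replacement under 11.1 moves the estimate more than censoring does in every case with unequal hazards.

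**The case against.** A reader might infer from 9.2 that patients with excessive toxicity drop out of PFS follow-up and are censored at their last evaluation. The documents do not support that as a statement of the plan. Section 11.2 recognises patients who stop treatment and keeps them in PFS, 9.1.3 calls for progression and death dates, and 12.03 calls for all forms. The censoring rule in 11.3.5 names patients lost to follow-up and is silent on those removed under 9.2. This part of the objection stands: for PFS there is an unresolved conflict, not a stated exit.

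A reader might also use the 16.7% in 11.3.1 to estimate how many patients would leave, 20 x 1/6 = 3.3. That figure is the prior mean for non-hematologic grade 4 toxicity after external beam radiotherapy starts. It is not a removal rate; removal is discretionary and its frequency is not given. The 16.7% row in the power table is therefore one point in an assumed range. Nor do the documents support a worked case in which all late toxicity falls in the removed patients.

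Finally, the toxicity that prompts removal is itself captured: attributable grade 3 or higher events are recorded under 11.3.2, and the safety rule is checked after every patient. That is correct, and it limits the loss to what happens later. Later effects are, however, what the long-term part of objective 3.2.1 is about.

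**Conclusion.** The point holds for late toxicity. As written, 9.2 ends study participation for toxicity, and nothing in the documents says that the assessments in 6.3.5, 6.3.6 and Table 2 of 6.4 continue. How many patients are affected cannot be derived from the documents.

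For PFS the finding is that 9.2, 11.1, 11.2 and 11.3.5 do not together say how a patient removed for toxicity is handled. Under the assumed shares and hazards the bias is 0.7 to 2.9 percentage points if these patients are censored (16.5% - 15.8% to 18.7% - 15.8%) and 1.4 to 6.3 points if they are excluded and replaced (17.2% - 15.8% to 22.1% - 15.8%). It is zero if their hazard equals that of the others. The stated 82% power reproduces and, like the toxicity stopping boundaries, is not called into question here. The point should be corrected because the gap is clear and cheap to close, not because bias has been shown.

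**What to change.** Leave the toxicity trigger and the investigators' discretion in 9.2 as they are; the change concerns data collection only.

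1. Amend 9.2 to say that a treated patient who comes off for toxicity remains in follow-up for the assessments in 6.3.5, 6.3.6 and Table 2 of 6.4, and for progression and survival, unless consent to follow-up is withdrawn. Time these assessments from the last treatment given, so that patients who do not complete therapy have a defined start.
2. When a patient or parent chooses to leave, record whether they agree to continued follow-up.
3. Reconcile 9.2 and the evaluability and replacement rule in 11.1 with 11.2, so that treated Stratum 1 patients who come off for toxicity stay in the PFS analysis. Rewording 9.2 alone would leave the 11.1 conflict in place.
4. Add to 11.3.5 how a patient who leaves under 9.2 and declines follow-up is censored.

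The cost is a short amendment to 9.2, 11.1 and 11.3.5, with visits already in the schedule continuing for a few more patients.
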